3.0 RESEARCH DESIGN AND METHODS

3.1 Drug/Device Information: NOT APPLICABLE

3.2 Type of Study: (Table 3: Individual Timeline): This is a longitudinal, efficacy randomized controlled trial (RCT). Veterans with MDD will be evaluated for eligibility and randomized to a 12-week intervention of a twice-weekly yoga and coherent breathing or walking group. As there is evidence that exercise improves mood in unipolar depression, the walking group will serve as an active control condition.(47) The policy for Common Data Elements will be incorporated into the data collection matrix. The Consolidated Standard of Reporting Trials (CONSORT) will be used to ensure the quality of reporting for this RCT.(48) The **primary dependent variable** will be changes in the Hamilton Depression Rating Scale (covering a 2 week period), and mood and anxiety scales (designed for repeated use, such that changes from pre to post intervention can be gauged), measured using valid and reliable psychological instruments obtained at screening, intervention weeks 4, 8, and 12, and before each MRS scan. The **secondary dependent variable** will be brain gamma amino-butyric acid (GABA) levels measured by magnetic resonance spectroscopy (MRS) in the left thalamus, the same region used in our prior studies.(9, 53, 65) The thalamus has the technical advantage of providing high quality spectra, has a high concentration of GABAergic neurons, and thus a high GABA signal, in which changes can be detected. The thalamus is also anatomically connected to other regions of interest. GABA levels will be measured by MRS in 3 separate scan acquisitions: before randomization (Scan 1), after 12-weeks of the yoga or walking intervention (Scan 2), followed immediately by the group assigned intervention and the final scan (Scan 3). The **third dependent variable** will be respiratory sinus arrhythmia (RSA) a component of heart rate variability (HRV) that is an accurate index of vagal influences on the heart.RSA will be measured before each scan and before and after an intervention at week 4, week 8 and week 12. Medications also are evaluated at weeks 4, 8, and 12. Two and six month follow-up phone calls will assess depression, quantity of yoga practice, and barriers to practice.

3.3.1. Sub-Study Participation: This is not a multisite study. There will be a contract with the McLean Hospital for goods and services regarding the imaging component of this study.

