- (8) If subjects have been taking antidepressants that target a monoamine system, the dose has been stable for at least one month with no anticipated changes during the study; or no antidepressants for one month
- (9) If subjects have been in a stable form of psychotherapy for three months, with no anticipated changes in their psychotherapy during the study (this would exclude time-limited manual-driven therapies such Cognitive Behavioral Therapy); or no psychotherapy for three months
- (10) Reliable contact information provided
- (11) Subject weighs up to 300 lbs. at the discretion of the PI.

(12) Subject has completed all required screening instruments and evaluations

3.3.2.6. Exclusion Criteria:

- (13) History of psychosis (substance-induced psychotic disorder and psychotic disorder due to another medical condition are allowable if fully resolved)
- (14) History of bipolar illness
- (15) History of suicidal ideation with intent in the last year according to the Columbia Suicide Safety Rating Scale (C-SSRS)
- (16) Subject has a history of suicidal attempt with intent to injure in the last year according to the C-SSRS.
- (17) Desire to be treated for MDD with a new treatment during the study such as pharmacotherapy somatic therapy or psychotherapy.
- (18) A contraindication to magnetic resonance evaluation (e.g., pregnancy, a cardiac pacemaker, ferrous implant including shrapnel, or intrauterine devices (IUDs) with copper, claustrophobia that would prevent scanning, some tattoos with black ink on the head including permanent eyeliner).
- (19) Current mind-body practice (e.g., yoga, Tai Chi, Qigong, breathing practices, or meditation) defined as more than 6 one-hour sessions in the last 6 months.
- (20) The use of intra-uterine devices with progesterone that interferes with the ability to determine the non-luteal phase required to schedule Imaging Session 1.
- (21) Participates in physical exercise > 5 hours/week that is equivalent to or greater than 6 metabolic equivalents (METs) in intensity.
- (22) Has been treated psychotropic medications such as mood stabilizers (e.g., Valproic Acid, Carbamazepine, or Lithium) in the last three months.

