Assessment of suicide risk is done using the Columbia Suicide Severity Rating Scale (CSSR-S). The development of suicidality with intent based on the CSSR assessment will result in study withdrawal such that the participant can receive additional conventional treatment. If a member of the research staff concludes that suicidality with intent is present they will develop a safety plan with the participant that can include support by friends or family, the inclusion of their medical treaters, being taken to the VABHCS Mental Health Clinic, where admission to an in patient unit can be arranged. If there is a safety concern after 3:30 when the Mental Health Clinic closes, participants will be referred to Urgent Care or the Lahey Clinic that provides after hours emergency services for the VABHCS. If the participant can be managed safely as an outpatient, arrangement will be made for follow-up treatment. It is noteworthy suicidality decrease in Phase 1 in civilians and no subject were withdrawn from the study for increased symptoms.

3.3.2.15. Potential Problems: Recruitment goals will be assessed every 6 months. If recruitment falls behind schedule, study staff will meet with the staff from the numerous clinic programs at the VABHCS to inform them of this research opportunity. If enrollment in the imaging component is behind due to nicotine use causing more than 10% of exclusions in a 6 month period, the inclusion criteria regarding smoking will be increased to include all subjects, regardless of abstinence.

3.3.2.16. Acquisition of Mood Scales and Psychological Tests: Participants will enter self-report mood and psychological scales onto paper forms. Investigator completed psychological mood and psychological scales will be entered into the REDCap database by research staff. The computers used for storage of mood scales and psychological tests will be VA computers.

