Hypothesis 4. a. Exploratory Concurrent Antidepressants: The yoga group but not the walking group will have a decrease in depressive symptoms regardless of antidepressant treatment at the beginning of the study.

Hypothesis 4. b. Exploratory PTSD Symptoms: If PTSD symptoms are present at screening, there will be a greater decrease in PTSD symptoms in the yoga compared to the walking group as measured by CAPS and PCL-C.

Hypothesis 4. c. Resting State Connectivity will increase over the course of the study with greater increases in the yoga group.

Hypothesis 4. d. Executive Function will increase over the study as measured by the Stroop, Digit Symbol test and fMRI activation.

3.5.2. Power Analysis for Depressive symptoms and Mood Scales: Based on the power analyses below, in order to achieve adequate power for all analyses, n=70 subjects, n=35 in the yoga and n=35 in the walking intervention must complete the interventions. Using Study 4 data in subjects with MDD in the LDG, the repeated measures ANOVA for EIFI scores from screening to the completion of the intervention did not reach statistical significance in the group of n=15 (baseline: 3.1 ± 2.2 and week-12: 3.9 ± 2.7 , $F_{1,13} = 1.097$, $p = 0.31$), a post hoc power analysis was conducted, which determined that the achieved effect size was $f = .281$, with 52% power. Based on this same effect size, an a priori power calculation was conducted, which determined that **n=35** subjects would be needed to detect significant differences for BDI-II, STAI, and EIFI scores from screening to the completion of the intervention, with effect size $f = .281$, with $< = .02$ to account for multiple comparisons, and 81% power. As the power analysis for the EIFI requires the largest number of subjects (n=70), which will be used to determine sample size. In order for 70 subjects to complete the intervention, assuming a 20% drop out, 84 subjects will be randomized.

3.5.3. Power Analysis for GABA: Consistent with our analytic plan for the longitudinal questions at-hand, we can compute the statistical power for Hypothesis II an analysis sample of **n=26** subjects in each of the study groups using the mixed linear model analogue of repeated measures analysis-of-

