4.6.1.10. Risk of Depression: This is a treatment study with modalities that are not approved for the treatment of depression. There are alternatives to participation, such as pharmacotherapy, psychotherapy or electroconvulsive, and subjects will be informed of these other options and of their right to withdraw from the study to seek conventional treatment. Subjects are screened for risk of suicide during the screening interview with the Columbia Suicide Safety Rating (C-SSR), a widely used instrument to assess suicide risk. It is noted that the C-SSR does not provide a score stating that the assessment of suicide is a clinical decision. For this reason, other than the development of suicidal ideation with intent, the decision to withdraw a subject remains a clinical matter that is informed by the assessments built into the study. There are assessments by a psychiatrist or member of the research staff licensed to assess for suicide risk at screening, and at the weeks 4, 8, and 12 assessments using the C-SSR. Safety Data from Study 4 showed that out of 30 subjects, 9 out of 10 subjects that endorsed suicidal ideation without intent at screening no longer endorsed suicidal ideation without intent at the end of the study. No subject developed suicidal ideation with or without intent during the study. Suicidal ideation with intent with in a year of screening was exclusionary. In addition, the C-SSR evaluation were in agreement with reports of self harm on the Beck's Depression Inventory II (BDI-II), consistent with both clinical evaluation and self-report with regards to safety being accurate. In the proposed study, staff will check question 9 of the BDI-II regarding self-harm before the participant

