A Randomized Control Trial Treating Depression With Yoga and Coherent Breathing Versus Walking in Veterans

NCT03489122

Document Date: 3-20-2017

D.17. Data Management and Analysis Plan: The Data Coordinating Center at the Boston University School of Public Health will provide data management, including the development and maintenance of a REDCap database and the creation of a final database that will be sent to [name] for statistical analysis, using SPSS 23.0. Descriptive statistics will be generated for baseline data and distributions between the yoga intervention and walking intervention will be compared using two-sample t-tests and chi-square or Fisher's exact tests to assess effectiveness of randomization. Descriptive statistics include means and standard deviations for continuous variables and group sizes and proportions for categorical variables. All analyses will be performed at the $\alpha = 0.05$ level of significance. Should groups have unequal distributions at baseline, relevant variables will be incorporated in subsequent linear models that will be used to examine intervention efficacy. In order to address the study aims of assessing the relative longitudinal change in dependent variables between yoga intervention and walking intervention groups over time, data will be collected at four time points, pre-randomization, and at weeks 4, 8, and 12. Mixed linear model analyses will be performed focusing on the group x time interaction for the primary effects to be statistically modeled. These analyses will allow for inclusion of data at differing numbers of time points per subject if needed. We will examine different within-subject correlation structures for our interaction model and determine the optimal structure by comparing Akaike information criteria (AIC) values. The correlation structure that yields the lowest AIC will be adopted. Subjects who change antidepressant medications during the study will be included in intent to treat analysis, but will be co-varied for medication changes. Potential cohort effects will be statistically addressed by controlling for group profiles, including group size, breakdown by sex of attendees, instructor, group parameters such as individual or group sessions, and group cohesion/overlap.

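### The only intent-to-treat analysis adjusts for antidepressant changes made after randomization, with no coding stated; depending on coding, this either does nothing useful for group x time or can move it off the effect of assignment (minor)

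*SAP*

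**What the plan says.** SAP D.17 and protocol 3.5.1 (Data Management and Analysis Plan) set out the same efficacy model in the same words: "Mixed linear model analyses will be performed focusing on the group x time interaction for the primary effects to be statistically modeled". The visits are pre-randomization and weeks 4, 8 and 12. On medication both say: "Subjects who change antidepressant medications during the study will be included in intent to treat analysis, but will be co-varied for medication changes".

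Neither says whether the covariate is ever/never, time-varying, a count, or crossed with time. Neither describes an analysis without it.

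Other parts of the protocol fix the timing. Inclusion criterion 8 (3.3.2.5) requires of anyone on a monoamine antidepressant that "the dose has been stable for at least one month with no anticipated changes during the study"; otherwise there must have been none for a month. Section 3.2 adds: "Medications also are evaluated at weeks 4, 8, and 12". The changes to be adjusted for are therefore essentially post-randomization events.

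Three passages bear on how common they will be. Exclusion 17 (3.3.2.6) rules out "Desire to be treated for MDD with a new treatment during the study such as pharmacotherapy somatic therapy or psychotherapy". Section 4.6.1.10 tells subjects of "their right to withdraw from the study to seek conventional treatment". Section 3.3.2.14 states: "The development of suicidality with intent based on the CSSR assessment will result in study withdrawal".

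**The concern.** An antidepressant change during follow-up can be a consequence of the assigned arm. Under 4.6.1.9 subjects may change their mind about conventional treatment at any time, and under 4.6.1.10 a report of worsening depression triggers an evaluation. Someone doing poorly in one arm may start or alter a drug and then improve.

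An as-assigned analysis counts that improvement as part of what followed from assignment. A model that conditions on the change may remove it, and then answers a different question from the one the intent-to-treat label implies. If the trigger is the response itself, conditioning can also distort the comparison when the drug does nothing.

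Because this is the only intent-to-treat model described, no unadjusted result stands beside it. With the coding open, it could also be settled after the data are seen.

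**Working it through.** **1. The plan's own figure.** The documents give no number for the medication covariate. The one stated power calculation built on group x time is for GABA (protocol 3.5.3): 26 per arm, yoga minus walking differences 0, 0.005 and 0.04, SD 0.06, within-subject correlation 0.65.
- The mean difference is 0.015, and the squared deviations sum to 0.000225 + 0.0001 + 0.000625 = 0.00095.
- Noncentrality = (26/2) x 0.00095 / (0.06² x 0.35) = 0.01235 / 0.00126 = 9.80, with 2 and 100 df. Power is 79.5%, against 80% stated.
- At correlation 0.70 power is 85.6%, against 85% stated.

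The figures reproduce and do not depend on the covariate.

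**2. Inputs.** From the documents: four visits, 35 completers per arm and 20% dropout (3.5.2), and correlation 0.65 (3.5.3, borrowed from GABA). Assumed: outcome SD 1 with lower scores better, a direct yoga effect of -0.50 SD at week 12, changes possible after weeks 4 and 8, and the change rates and drug effects below. The standard error of the week-12 contrast is sqrt(2 x 2 x (1 - 0.65)/35) = 0.20 SD.

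**3. Time-constant main effect.** The same amount is added to a subject's score at every visit, so it cancels from each within-subject difference, and group x time is estimated from those differences. With complete data the simulated estimate was unchanged to within 2e-12. With 20% random dropout, on a scale where the standard error was 1.60 points, the mean absolute shift was 0.06 points (about 4% of a standard error). The largest shift in one data set was 0.38, and there was no systematic direction.

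**4. Time-varying term.** Let D be the drug benefit in SD, and pY and pW the proportions changed by week 12 in yoga and walking. With changes random within arm:
- as-assigned effect = -0.50 - D(pY - pW);
- the time-varying model returns about -0.50;
- shift (adjusted minus as-assigned) = D(pY - pW).

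Simulation used 100,000 per arm and an unstructured covariance; its sampling error is about 0.004.

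| Yoga v walking changing | D | Shift by formula | As-assigned, simulated | Time-varying, simulated |
|---|---|---|---|---|
| 2% v 6% | 0.3 | -0.012 | -0.490 | -0.502 |
| 5% v 15% | 0.3 | -0.030 | -0.463 | -0.493 |
| 10% v 30% | 0.5 | -0.100 | -0.401 | -0.500 |
| 30% v 10% | 0.5 | +0.100 | -0.593 | -0.492 |
| 15% v 15% | 0.5 | 0 | -0.505 | -0.504 |

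With response-driven changes in about 20% of subjects and no drug effect, the estimate stayed at -0.499.

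**5. Change-by-time term.** With random changes it behaves like the time-varying term. With response-driven changes and no drug effect it still moves:
- about 5% changing: -0.499 to -0.486 (0.013 SD);
- about 20% changing: -0.499 to -0.468 (0.031 SD);
- about 20% changing, random-slope data: -0.493 to -0.445 (0.048 SD).

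**6. Cross-check on a points scale.** Assumed: SD about 5.9, correlation 0.5, direct yoga effect -4, and a 40% chance of change when the score exceeds 18 at week 4 or 8. In the large sample 26.2% of walking and 18.9% of yoga subjects changed, a gap of 0.073. For drug effects of -2, -4 and -6, the as-assigned estimates were -3.82, -3.67 and -3.52. Both time-dependent codings gave -3.97 each time. The shifts of 0.15, 0.29 and 0.44 (rounded) match 0.073 x 2, 4 and 6. At 35 per arm with drug effect -6, the rejection rate was 0.62 unadjusted and 0.80 with the time-varying term, because the two models estimate different effects.

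**7. Leaving the coding open.** With no yoga effect, 35 per arm and 10,000 trials per setting, taking the smallest p of the three codings gave a type I error of 5.5% to 5.9%, against 4.6% to 4.9% for any single coding (Monte Carlo error about 0.2 points).

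**The case against.** The strongest reply is that little will happen in practice. The plainest reading of the sentence is a time-constant main effect, which is harmless. Entry rules select people on stable treatment who do not want a new one, and some who later seek treatment will withdraw instead. At 2% v 6% changing, the shift is 0.012 SD, about 6% of a standard error. The 0.10 SD figure needs a 10% v 30% split and a 0.5 SD drug effect, and the documents supply neither. On this view, stating the coding would be enough.

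The argument about size stands and sets the severity. It does not rescue the sentence: one coding is idle for the primary term, and the others can change what is estimated. Stating the coding would settle which of these applies without giving an unadjusted as-assigned result.

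A reader might infer three stronger things that the documents do not support.
- **That any time-dependent coding biases the result.** The time-varying term needs both a drug effect and unequal change by arm. The change-by-time term needs one of two things: unequal change with a drug effect, or response-driven change. The documents establish none of these.
- **That a main effect is exactly inert in this trial.** That is true only with complete data, and the plan expects dropout and unequal numbers of visits.
- **That the next sentence of SAP D.17, on controlling for instructor and group cohesion, makes group x time inestimable.** That would require leaders nested within arm and entered as fixed effects that vary with, or are crossed with, time. No passage gives leader numbers or such a coding, so it is not part of this point.

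**Conclusion.** The concern holds as a minor one. A post-randomization variable that may depend on response sits in the only intent-to-treat model, with its coding open. As a main effect it has no useful role for group x time. As a time-varying or change-by-time term it can move the estimate away from the effect of assignment, in either direction.

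The plausible size runs from about 0.01 SD, when few change, to about 0.10 SD, when changes are common, differ by 20 percentage points between arms and carry a 0.5 SD drug effect. The latter is half a standard error at 35 per arm. Every size rests on assumed change rates and drug effects, on a correlation borrowed from the GABA calculation, and on the assumed timing of changes. The type I error cost of choosing the coding late is about one percentage point or less. None of this shows that the trial's result will be biased; it shows that the sentence allows it at no benefit to the primary test.

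**What to change.** In SAP D.17 and protocol 3.5.1:
- Delete the clause after the comma in the medication sentence, so that the primary analysis is not adjusted for medication change.
- State that all outcome data are analysed as assigned regardless of medication change, without post-randomization covariates.
- Report medication changes by arm, from the week 4, 8 and 12 reviews.
- Move the medication-adjusted model to a labelled sensitivity analysis, with its coding fixed before the data are seen.

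The cost is wording in two documents and one extra model. No new data are needed, since medications are already reviewed at those visits. The plan's separate rule on baseline variables found unequal between groups is not affected.
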